**Table 6.1 Schedule of Study Procedures and Assessments**

Table 6.1 Schedule of Procedures and Assessments						
Test/study	Screening	Cycle 1 to Cycle 5 a	Cycle 6 f and future cycles	End of Treatment g	Follow-up visits h	Survival Follow-up v
	Day -30 to -1	Day 1 (+/- 3)	Day 1 (+/- 3)	28 days (+/- 7) after last dose	12 month Follow-up	48 Month Follow-up
Informed consent	X					
Baseline conditions b	X					
Quality of life assessments c	X		X	X	X	
AE assessment d		X	X	X	X	X v
Concomitant medications and procedures	X	X	X	X	X	
Treatment/Drug Administrationf						
Nivolumab		X	X			
Radiation therapy		X				
Cisplatin		X				
Clinical proceduresg						
Physical exam h	X	X	X	X	X	
Vital signs	X	X	X	X	X	
Medical history	X	X				
Disease assessment i	X	X		X	X	
ECOG	X	X	X	X	X	
Measurable disease j	X	X		X	X	
Biopsy or archived tissue procurement k	X	X				
Laboratory proceduresl						
CBC w/ Diff m	X	X u	X	X	X	
Blood chemistry n	X	X u	X	X	X	
Fasting Glucose n	X	X u	X	X	X	
TSH evaluation n	X	X u	X	X	X	
Urinalysis n	X					
Pregnancy test (Serum or urine HCG) o	X					
Tissue for exploratory research p	X	X				

**Table 6.1 Schedule of Study Procedures and Assessments**

Table 6.1 Schedule of Procedures and Assessments						
Test/study	Screening	Cycle 1 to Cycle 5a	Cycle 6f and future cycles	End of Treatmentg	Follow-up visitsh	Survival Follow-upv
	Day -30 to -1	Day 1 (+/- 3)	Day 1 (+/- 3)	28 days (+/- 7) after last dose	12 month Follow-up	48 Month Follow-up
Blood for exploratory research q	X	X	X	X	X	
Imaging proceduresr						
Whole body PET-CT r	X			X	X	
MRI r nasopharynx/face/neck	X			X	X	

a Each 14-day period of treatment will represent 1 cycle and begins from C1D1.b Baseline conditions assessmentc As part of efficacy assessments, quality of life by FACT-NP, FACT-Taxane, HHIE-S, and EuroQOL EQ-5D will be administered at baseline, at cycle 6, at end of treatment and at all followup visits. Survey's not available in the patient's language may be administered by the study staff in an interview format with a translator, however failure to obtain any individual quality of life survey not available in the patient's language will not be considered a protocol deviation.d Toxicity will be assessed by CTCAE v5.0f There is a 72 hour window of scheduled nivolumab administration. **In Dose Schedule 1:** Nivolumab will be administered on C1D1 for priming and then q14 days beginning C2D1, concurrent with chemoradiation, until C5D1. Nivolumab will not be administered on C6D1 to allow for any resolution of toxicities. Beginning C7D1, adjuvant nivolumab q14 days will be administered until C12D1. **In Dose Schedule 2:** Nivolumab will be administered on C1D1 concurrent with chemoradiation (no priming), and then q14 days until C4D1. Nivolumab will not be administered on C5D1 to allow for any resolution of toxicities. Beginning C6D1, adjuvant nivolumab q14 days will be administered until C11D1. **In Dose Schedule 3:** Nivolumab will not be administered until after completion of chemoradiation. Beginning C6D1, adjuvant nivolumab q14 days will be administered until C11D1. Immune-related toxicities should be at grade 1 or lower prior to starting a patient on the adjuvant phase of therapy; if not, initiation of the adjuvant phase should be delayed until resolution of toxicities.h Physical Exam includes weight measurementsi Disease-specific criteria (for CRF purposes, e.g.: GU assessment, BR disease Eval, AML-MDS Summary, etc.)j Measurable disease will be assessed using RECIST 1.1 criteriak For the **baseline** tissue collection, if a biopsy was performed within 90 days prior to C1D1, and no intervening treatment was given, a repeat biopsy is not required if adequate tumor tissue can be provided. **Repeat biopsy** will be at the discretion of the investigator, and timing will depend on Dose Schedule. **In Dose Schedule 1:** Tumor tissue post-nivolumab during cycle 1 AND after first week of radiation therapy. **In Dose Schedule 2 and 3:** Tumor tissue after first week of radiation therapy only. See appendix 4 for further details.l All blood draws may be completed within 7 days prior to start of therapy unless otherwise specified; screening labs must be completed within 14 days of Cycle 1 Day 1.m Hemoglobin, hematocrit, platelets, total white blood cell count (WBC) and differentialn Alkaline phosphatase, aspartate aminotransferase/alanine aminotransferase (ALT/AST), total bilirubin, total protein, albumin, calcium, phosphorus, magnesium, blood urea nitrogen (BUN), creatinine, glucose fasting), potassium, sodium, chloride, bicarbonate, uric acid, LDH, fasting lipid panel (LDL, total cholesterol, triglycerides), thyroid stimulating hormone (TSH).o **Pre-menopausal females:** serum or urine pregnancy test within 7 days prior to start of study drug. Serum pregnancy test by local laboratory  $\leq$  1 day prior to C1D1 for women of childbearing potential. If the serum pregnancy test results are not available on C1D1, a urine pregnancy test can be performed on C1D1 to confirm that the patient is not pregnant prior to dosing.p See Appendix 4 for details on tissue specimen collection and processing.q Collection of peripheral blood for correlative biomarkers and peripheral immune changes must be collected with every cycle of nivolumab. Blood will also be collected in post-treatment followup to 1 year.r Imaging with MRI nasopharynx/face/neck and whole body PET-CT will be performed at screening and at end of treatment and at 1 year followup, with further imaging to be performed as clinically indicated.

- If a whole body PET-CT (top of head to mid-thigh) scan (preferred) or a CT of the chest, abdomen, and pelvis was performed within 60 days prior to C1D1, then a repeat scan is not required provided the images are adequate for analysis. PET-CT is required after protocol treatment completion.

- MRI scan of nasopharynx/face/neck required within 60 days prior to C1D1 and after protocol treatment completion.
- sAll patients to be followed for safety until the EOT visit. This visit should occur 28 (+/-7) days after the last dose of nivolumab. Patients with ongoing SAEs will be followed until either resolution or stabilization of the event(s) have been determined.
- tAfter completion of all treatment, patient will be followed at 1, 3, 6, 9 and 12 months +/- 1 week for up to 1 year.
- uFasting lipid panel and TSH blood tests will not be performed on day 8. Only CBC with differential and blood chemistry tests including non-fasting glucose are required on day 8 of Cycles 2, 3, and 4.
- vSurvival follow-up information may be collected via telephone calls, and/or review of the medical record, every 3 months for an additional 4 years. Survival and disease status will be collected until participant death, withdrawal, or if the participant is lost to follow-up.

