#### **Management/Next Dose for Nivolumab**

No change in dose\*

Grade 2	No change in dose; see guidelines for management in Appendix 5.
Grade 3	Hold* until $\leq$ Grade 1; see guidelines for management in Appendix 5. Resume at same level at investigator discretion
Grade 4	Off protocol therapy

\*Patients with purpuric or bullous lesions must be evaluated for vasculitis, Steven-Johnson syndrome, TEN, and autoimmune bullous disease including oral lesions of bullous pemphigus/pemphagoid. Pruritus may occur with or without skin rash and should be treated symptomatically if there is no associated liver or GI toxicity. Note skin rash typically occurs early and may be followed by additional events particularly during steroids tapering.

Liver Function	Management/Next Dose for Nivolumab
AST/ALT/T. Bili *	
$\leq$ Grade 1	No change.
Grade 2	Hold until UNL or baseline. Resume at same dose schedule; see guidelines for management in Appendix 5.
Grade 3	Off protocol therapy; see guidelines for management in Appendix 5.
Grade 4	Off protocol therapy see guidelines for management in Appendix 5.
Continued treatment of active immune-mediated hepatitis may exacerbate ongoing inflammation. Holding drug to evaluate LFT changes and early treatment are recommended. LFT changes may occur during steroid tapers from other events and may occur together with other GI events including cholecystitis/pancreatitis.	

Renal Function	Management/Next Dose for Nivolumab
Serum Creatinine	
$\leq$ Grade 1	Continue treatment.
Grade 2	Hold until UNL or baseline. Resume at same dose schedule; see guidelines for management in Appendix 5.
Grade 3	Hold until UNL or baseline. Resume at same dose schedule; see guidelines for management in Appendix 5.
Grade 4	Off protocol therapy

For Grade 2 or greater, consider renal biopsy.

Diarrhea/ Colitis	Management/Next Dose for Nivolumab
$\leq$ Grade 1	No change in dose; see guidelines for management in Appendix 5.
Grade 2	Hold until Grade 0 or baseline; see guidelines for management in Appendix 5.
Grade 3	Off protocol therapy; see guidelines for management in Appendix 5.
Grade 4	Off protocol therapy; see guidelines for management in Appendix 5.
See GI AE Algorithm for management of symptomatic colitis (in IB).	
Patients with grade 2 symptoms but normal colonoscopy and biopsies may be retreated after resolution.	

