Patients with persistent symptoms greater than 14 days who require steroids should be taken off study treatment.	
Please evaluate pituitary function prior to starting steroids if possible without compromising acute care.	
Evaluation for all patients for additional causes includes C. diff , acute and self-limited infectious and foodborne illness, ischemic bowel, diverticulitis, and IBD.	

Pancreatitis	Management/Next Dose for Nivolumab
Amylase/Lipase	
$\leq$ Grade 1	Hold dose until grade 0.

Grade 2	Hold until Grade 0. Resume at same dose schedule if asymptomatic.
Grade 3	Hold* until Grade 0. Resume at same dose schedule if asymptomatic. Patients who develop symptomatic pancreatitis or DM should be taken off treatment.*
*Grade 4	Off protocol therapy
	Patients may develop symptomatic and radiologic evidence of pancreatitis as well as DM and DKA. Lipase elevation may occur during the period of steroid withdrawal and with other immune-mediated events or associated with colitis, hepatitis, and patients who have asymptomatic lipase elevation typically have self-limited course and may be retreated. For treatment management of symptomatic pancreatitis please follow the Hepatic Adverse Event Management Algorithm (in Appendix 5).
	*Excluding asymptomatic amylase and lipase increases

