##### 6.1.1.1 Screening Assessments

Patients will undergo screening assessments within 30 days before receiving the first dose of nivolumab, unless otherwise noted. Study procedure-related AEs that occur after signing of the

Informed Consent Form (ICF) and before administration of nivolumab will also be collected.

The Screening procedures and assessments must be completed within 30 days prior to the Cycle 1 Day 1 Visit, unless otherwise noted.

- Physical examination
- Weight
- Vital signs
- Complete medical history
- Baseline conditions assessment
- Disease Assessment
- ECOG Performance status
- History of prior treatments and any residual toxicity relating to prior treatment
- Concomitant medications and procedures
- Biopsy or archived tissue procurement
  - Archived tissue: If no intervening treatment received, adequate tissue available, and performed within 90 days of day 1 (cycle 1 day 1) of study treatment; otherwise, fresh biopsy required. See Appendix 4.
- Complete blood count (CBC) with differential and platelet count (within 14 days of Cycle 1 Day 1)
- Serum chemistry assessment (within 14 days of Cycle 1 Day 1), including:
  - Alkaline phosphatase, aspartate aminotransferase/alanine aminotransferase (ALT/AST), total bilirubin, total protein, albumin, calcium, phosphorus, magnesium, blood urea nitrogen (BUN), creatinine, glucose (fasting), potassium, sodium, chloride, bicarbonate, uric acid, LDH, fasting lipid panel (LDL, total cholesterol, triglycerides).
- Serum or urine pregnancy test within 7 days prior to the start of study drug in pre-menopausal females.
- TSH evaluation (within 14 days of Cycle 1 Day 1)
- Urinalysis (within 14 days of Cycle 1 Day 1)
- MRI of nasopharynx, face, and neck within 60 days prior to start of study drug.
- Whole body PET-CT of top of head to mid-thigh (preferred) or CT of chest, abdomen, and pelvis within 60 days prior to the start of study drug.
- Research blood draw: collection of peripheral blood for EBV DNA and correlative biomarker studies.
- All blood draws may be done within 7 days prior to start of therapy unless otherwise specified.
- Contraceptive counseling
- Serum pregnancy test (by local laboratory) ≤ 1 days prior to the first day of dosing for women of childbearing potential. If the serum pregnancy test results are not available on C1D1, a urine pregnancy test can be performed on C1D1 to confirm that the patient is not pregnant prior to dosing.
- Baseline quality of life assessments

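### Nivolumab is held by amylase/lipase grade, but neither analyte is a scheduled test, so holds for asymptomatic rises depend on local testing and there is no required baseline to judge them against.

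*Combined protocol and SAP*

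**What the plan says.** **The dosing rule.** The pancreatitis (amylase/lipase) table in Section 5.2.1 has four rows.

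- Grade 1 or lower: "Hold dose until grade 0".
- Grade 2: "Hold until Grade 0. Resume at same dose schedule if asymptomatic". Being free of symptoms governs resumption, not the hold.
- Grade 3: also a hold to grade 0, with treatment stopped for symptomatic pancreatitis or diabetes.
- Grade 4: off protocol therapy.

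A note, "Excluding asymptomatic amylase and lipase increases", is keyed by asterisk. As printed, the asterisks stand at the grade 3 and grade 4 rows only. The table also says that patients with "asymptomatic lipase elevation typically have self-limited course and may be retreated". Section 5.2.1 gives these specific tables precedence over the general grade guideline, and confines delays to toxicity that the treating physician considers related to study drug.

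**The schedule.** The screening chemistry in 6.1.1.1 is itemised down to "uric acid, LDH, fasting lipid panel (LDL, total cholesterol, triglycerides". Footnote n of Table 6.1 gives the same list for scheduled visits and adds TSH: "potassium, sodium, chloride, bicarbonate, uric acid, LDH, fasting lipid panel (LDL, total cholesterol, triglycerides), thyroid stimulating hormone (TSH". Neither contains amylase or lipase. The procedure lists in 6.1.2.1, 6.1.3 and 6.1.4 say only serum chemistry, and footnote u adds neither analyte on day 8.

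**Neighbouring rows.** The liver (grade 2) and renal (grades 2 and 3) rows read "Hold until UNL or baseline. Resume at same dose schedule; see guidelines for management in Appendix 5". The grade 2 diarrhea row reads "Hold until Grade 0 or baseline; see guidelines for management in Appendix 5". The lowest pneumonitis row also allows return to baseline. The amylase/lipase row does not.

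**The concern.** A dosing rule that acts on a laboratory value needs that value to be available in the same way for every patient. Testing for cause will find rises in patients with symptoms. It will generally miss rises without symptoms, which the two lower rows also cover as printed. In a multicenter trial, two patients with the same asymptomatic grade 1 lipase rise could be treated differently, one held and one dosed, because of local laboratory habit.

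The lack of a baseline matters separately. A rise known to predate nivolumab would not be drug-related and would not trigger a hold. Without a required pre-treatment value, the physician may not know that it predates treatment. If such a rise is then judged drug-related, the row asks for grade 0, a level the patient may not have had at entry.

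At stake are even application of dose holds and the completeness of one laboratory abnormality under the secondary safety endpoint in 2.4.2.

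**Working it through.** **1. Required measurements.** Reading every laboratory list (6.1.1.1, 6.1.2.1, 6.1.3, 6.1.4, Table 6.1 with its footnotes, Appendix 4), the number of required amylase or lipase measurements is 0 at screening, 0 on treatment, 0 at end of treatment and 0 in follow-up. The liver and creatinine tables act on analytes that footnote n does schedule.

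**2. How many patients.** Section 1.2.3.3 classes lipase increased and amylase increased each as common with monotherapy, defined there as at least 1% and under 10%. Expected patients = 40p.

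| p | 40p |
|---|---|
| 0.01 | 0.4 |
| 0.05 | 2 |
| 0.10 (upper limit) | 4 |

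These are per analyte and any grade. Applying monotherapy rates to this combination is an assumption.

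**3. Under-ascertainment (illustration).** Assume p = 0.05, so 2.0 expected cases, and let t be the share of affected patients who happen to be tested while raised. Found = 2t: 0.5, 1.0 and 1.5 at t = 0.25, 0.50 and 0.75. The documents give no value for t. Section 8.5 defines the safety population, so the denominator is known; the reported rate of asymptomatic rises would be a lower bound.

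**4. Run-in.** A schedule change needs 3 or more of 6 patients with a DLT. Taking the extreme case that every rise counted as a DLT, P(X ≥ 3), with X binomial(6, p), is 0.00002 at 1%, 0.0022 at 5% and 0.0159 at 10%. The true effect is smaller, since DLTs require a grade 3 or higher immune-related event, a long hold, or an immune-related interruption or failure of chemoradiation.

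**5. The hold clock.** Section 5.2.1 restarts dosing at the next two-week point. Counting from the missed dose, the restart points are day 14 and day 28. Section 6.1.2.1 allows a 72-hour window and Table 6.1 allows ±3 days, so the second point can be dosed from 28 − 3 = day 25. That is inside both statements of the limit in Section 5.2.1 (28 days under Discontinuation Criteria, more than 28 days elsewhere). A patient who clears by then need not breach it.

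**6. What routine testing would do if the low-grade hold stayed.** This bears on the choice of fix. Section 8.2.1 stops at 11 or fewer completions of 22 and rejects the null at 26 or more of 40. Its exact power at a true rate of 0.70 is 0.803, matching the stated 80%. Let g be the assumed share of rises that lead to a hold reaching the limit. Completion = 0.70 × (1 − p·g); for example, at p = 0.05 and g = 0.25 it is 0.70 × 0.9875 = 0.691. Power is then:

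| p | g = 0.10 | g = 0.25 | g = 0.50 |
|---|---|---|---|
| 0.01 | 0.800 | 0.796 | 0.789 |
| 0.05 | 0.789 | 0.767 | 0.728 |
| 0.10 | 0.774 | 0.728 | 0.644 |

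These are costs of adding routine tests without relaxing the low-grade hold. They are not losses under the current plan.

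**The case against.** Testing for cause is a legitimate design. The row is headed pancreatitis, and a dose rule says what to do when an event is found; it does not oblige the trial to screen for it. Other rows also rely on unscheduled tests: baseline pO2 for pneumonitis, CPK for fatigue, and adrenal assessment. This stands, and it is why the fix does not require routine on-treatment testing. It does not explain why the two lower rows, as printed, act on rises without symptoms.

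The asterisk reading can be questioned. Elsewhere in 5.2.1 an asterisk on a hold points to the 28-day footnote, and excusing asymptomatic grade 3–4 rises while holding grade 1 would be odd. Section 3.2 also lets the adjuvant phase start with immune-related toxicity at grade 1 or lower. Loose drafting is a fair explanation. Even so, the scope of the exclusion is unclear to a site, and wording is the remedy.

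A reader might infer that a patient with a pre-existing rise is locked out of treatment, or must stop at the second two-week point. The documents do not support that. The table says asymptomatic lipase rises may be retreated. Section 5.2.1 lets the investigators and the Principal Investigator agree to continue past 28 days. It also exempts certain grade 3–4 laboratory abnormalities without organ pathology, and isolated grade 4 amylase or lipase values that fall within a week. The visit window avoids an automatic breach. These provisions soften the rule, but none sets a resumption threshold for a pre-existing low-grade rise.

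**Conclusion.** The mismatch between rule and schedule is real. Holds for asymptomatic amylase or lipase rises depend on whether a site tests, the drug-relatedness judgement has no required baseline, and the row lacks the return-to-baseline term used in comparable rows. The size is modest: roughly 0.4 to 4 of 40 patients per analyte, assuming the monotherapy frequency class applies, with an unknown share going undetected.

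It would be tempting to carry this through to the run-in decision or the primary endpoint. The documents do not support that. Even the extreme run-in case gives at most about 0.016, the effect on completion under the current plan is small, and the safety denominator is defined. The change is worth making because it is cheap and makes a stated dosing rule work the same way at every site.

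**What to change.** 1. Add amylase and lipase to the screening chemistry in 6.1.1.1.
2. Change the resumption term in the amylase/lipase rows to grade 0 or baseline, with baseline being the screening value.
3. State that the row applies to symptomatic or clinically indicated testing, and that an asymptomatic grade 1 rise does not require a hold.

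**Cost.** One screening panel per patient, about 40 in all, on blood already drawn, plus the wording. The downside is a small laboratory cost, and asymptomatic rises remain under-ascertained.

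**Optional.** The sponsor may prefer fuller ascertainment by testing on day 1 of each nivolumab cycle. From footnote f, Dose Schedules 1, 2 and 3 give 11, 10 and 6 doses. With screening, that is 40 × 12 = 480, 40 × 11 = 440 or 40 × 7 = 280 panels. This should not be added with the low-grade hold unchanged, because it would generate extra holds that could count against completion.

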## 6.2 Prohibited Medications

### Permitted Therapy

Subjects are permitted to use topical, ocular, intra-articular, intranasal, and inhalational corticosteroids (with minimal systemic absorption). Physiologic replacement doses of systemic corticosteroids are permitted, even if  $> 10$  mg/day prednisone equivalents. A brief course of corticosteroids for prophylaxis (eg, contrast dye allergy) or for treatment of non-autoimmune conditions (eg, delayed-type hypersensitivity reaction caused by contact allergen) is permitted.

Intravitreal injections of vascular endothelial growth (VEGF) inhibitors are permitted if used according to the approved ocular indication, such as macular degeneration.

## 7 Reporting and Documentation of Results

### 7.1 Evaluation of Efficacy (or Activity)

#### 7.1.1 Antitumor Effect – Solid Tumors

A secondary measure of response to neoadjuvant therapy in this study will be determined by RECIST 1.1 criteria according to the new international criteria proposed by the Response Evaluation Criteria in Solid Tumors ([RECIST](#)) Committee [JNCI 92(3):205-216, 2000]. Changes in only the largest diameter (unidimensional measurement) of the tumor lesions are used in the RECIST v1.1 criteria (or [International Workshop on Chronic Lymphocytic Leukemia \[IWCLL\]](#)). RECIST 1.1 will also be used to determine whether the patient has progressive disease in the adjuvant portion and follow-up portion of the study in accordance with standard of care practices.

#### 7.1.2 Definitions

##### Evaluable for toxicity

All patients will be evaluable for toxicity from the time of their first treatment with the study drug.

##### Evaluable for objective response

Only those patients who have measurable disease present at baseline, have received at least one cycle of therapy, and have had their disease re-evaluated will be considered evaluable for response. These patients will have their response classified according to the definitions stated below. (Note: Patients who exhibit objective disease progression prior to the end of Cycle 1 will also be considered evaluable.)

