### **6.1.2 Treatment Period**

During the Treatment Period subjects will receive nivolumab until the period of adjuvant therapy is complete, disease progression, the occurrence of unacceptable drug-related toxicity or for other reason(s) such as subject withdrawal. Subjects should be instructed to immediately inform the principal investigator (PI) of any AEs. Patients will be monitored for AEs from the time the first dose of nivolumab is administered through 30 days after the last dose.

Nivolumab will be administered to patients every 2 weeks through the intravenous route. Each 14-day period of treatment represents 1 cycle, with dosing initiated on C1D1. No dose escalation beyond the starting dose is allowed.

Patients will undergo serial assessments for anti-tumor efficacy and drug safety. Tumor samples will be collected at baseline and after the first cycle of nivolumab at the investigator's discretion. Serial blood sampling will be conducted for longitudinal immunologic assessment (see Appendix 4). Radiologic scans will be acquired by the investigative site and evaluated locally for patient treatment decisions. Patients will be followed with monthly clinical and laboratory assessments while on protocol-mandated treatment, as well as routine physical examinations every 3 months and scans at the end of treatment and 12 months to assess for disease status for a 1 year period following completion of all treatment.

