### **8.4.3 Secondary Analysis (or Analysis of Secondary Endpoints)**

**Objective Response Rate (ORR):** The ORR is based on the best overall response (BOR) recorded from the first day of treatment until time of assessment. The frequency and percentages of patients with a best overall response rate of complete response (CR), partial response (PR), stable disease (SD), or progressive disease (PD) will be determined.

**Locoregional Control (LRC) Rate:** Duration of LRC will be calculated as 1+ the number of days from the first day of treatment to time of documented locoregional clinical or radiographic relapse, progression or death due to any cause. For patients who continue treatment post-progression, the date of clinical or radiographic relapse or progression will be used for analysis. The Kaplan-Meier analysis will be used to calculate the mean LRC rate with 95% confidence interval.

**Distant Metastasis (DM) Rate:** Time to DM will be calculated as 1+ the number of days from the first day of treatment to documented clinical or radiographic progression at a distant metastatic site, or death due to any cause. Pathologic confirmation is not required to document the date of distant progression. For patients who continue treatment post-progression, the date of clinical or radiographic progression will be used for analysis. The Kaplan-Meier analysis will be used to calculate the mean DM rate with 95% confidence interval.

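### Treated patients with no documented re-evaluation drop out of the response-evaluable set, and the ORR analysis names no denominator that would bring them back

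*Combined protocol and SAP*

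**What the plan says.** Section 7.1.2, under Evaluable for objective response, sets three conditions: measurable disease at baseline, at least one cycle of therapy, and a re-evaluation. Only patients who meet the first two "and have had their disease re-evaluated will be considered evaluable for response". A note adds one exception: "Patients who exhibit objective disease progression prior to the end of Cycle 1 will also be considered evaluable".

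Section 8.4.3 defines the endpoint: "The ORR is based on the best overall response (BOR) recorded from the first day of treatment until time of assessment". It then asks for counts and percentages of CR, PR, SD and PD. It does not say which patients form the denominator, has no category for patients without an assessment, and gives no rule for a missing response.

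On timing, the imaging footnote of Table 6.1 says "Imaging with MRI nasopharynx/face/neck and whole body PET-CT will be performed at screening and at end of treatment and at 1 year followup". The same footnote leaves room for unscheduled scans at the investigator's judgement. Section 6.1.2 agrees on the schedule: "scans at the end of treatment and 12 months to assess for disease status". A Table 6.1 footnote ties the end-of-treatment visit to the last dose: "This visit should occur 28 (+/-7) days after the last dose of nivolumab". Table 6.1 also marks a measurable-disease row, assessed by RECIST 1.1, in the Cycle 1 to Cycle 5 column, where neither MRI nor PET-CT is marked.

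The population is described differently elsewhere. Section 8.2.5 calls a patient evaluable after any amount of study drug. Section 8.4.1 requires at least one cycle at the MTD schedule, but only for the primary endpoint. Inclusion criterion 7 in section 3.5.1 requires measurable disease at entry.

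**The concern.** Being re-evaluated is a post-baseline event. It depends on the patient staying alive and on study until someone measures the tumour. A set defined by that event is selected on something related to outcome. Patients who die, withdraw consent or are lost before any assessment fall out of both numerator and denominator, as do those who receive less than one cycle and do not progress. If they respond less often than the patients who remain, the reported ORR is too high. Because the trial has a single arm, no control group carries the same distortion. The ORR will be read against outside experience, where a shift of several points matters.

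**Working it through.** **The plan's own figures.** The documents give no expected ORR, ORR precision or rate of missing assessments, so there is no ORR figure to reproduce. The figure that can be checked is the primary design in section 8.2.1: 22 patients, continue with 12 or more completions, then reject the null at 26 or more of 40. The probability of rejecting is the sum over x = 12 to 22 of P(Bin(22, p) = x) × P(Bin(18, p) ≥ 26 − x). At p = 0.7 this is 0.803, which reproduces the stated 80% power. At p = 0.5 it is 0.0396, so the stated 0.05 holds as an upper bound. None of this depends on ORR.

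**When the first scheduled scan falls.** These dates assume no delays and use the dosing footnote of Table 6.1.
- Schedule 1: the last dose is at Cycle 12 Day 1, which is 11 × 14 = 154 days after Cycle 1 Day 1. Adding 28 ± 7 days gives 175 to 189 days, or 25 to 27 weeks (nominally 26).
- Schedules 2 and 3: the last dose is at Cycle 11 Day 1, 140 days after Cycle 1 Day 1. Adding 28 days gives 168 days, or 24 weeks nominally.
- A patient who stops nivolumab early reaches the visit earlier, because it is counted from the last dose.

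**Who leaves the set and who stays.**
- Stays: objective progression before the end of Cycle 1 (by the note); later documented progression (itself a re-evaluation, classed as PD); a patient who stops for toxicity but attends the end-of-treatment scan.
- Leaves: death, withdrawal or loss before any documented re-evaluation; less than one cycle without objective progression.

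**Size.** Let N be the treated patients, x the responders and k the treated patients never re-evaluated, all taken to be non-responders. The inflation is x/(N − k) − x/N. N = 40 is the section 8.2.1 maximum; x and k are assumptions.

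| x | All treated, x/40 | k = 2, x/38 | Difference | k = 4, x/36 | Difference |
|---|---|---|---|---|---|
| 24 | 60.0% | 63.2% | 3.2 | 66.7% | 6.7 |
| 28 | 70.0% | 73.7% | 3.7 | 77.8% | 7.8 |
| 32 | 80.0% | 84.2% | 4.2 | 88.9% | 8.9 |
| 36 | 90.0% | 94.7% | 4.7 | 100.0% | 10.0 |

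With k = 0 the difference is zero in every row. For x = 28, the exact 95% intervals are 53.5% to 83.4% for 28/40 and 60.8% to 89.9% for 28/36.

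Sections 8.2.3 and 8.2.4 still describe 28 patients. At that size, with x = 21, the rate of 21/28 = 75.0% becomes 21/26 = 80.8% (k = 2) or 21/24 = 87.5% (k = 4).

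**The case against.** A reader might infer that early treatment failures in general vanish from the ORR, or that everyone who stops early goes unscanned for some six months. The documents do not support either. Documented progression is retained at any time, extra imaging is allowed when clinically indicated, and the end-of-treatment scan moves forward with the last dose. Nor does non-completion of adjuvant nivolumab measure the problem. The design's alternative implies 0.3 × 40 = 12 non-completers, but most of them may still be scanned.

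Table 6.1 also schedules a RECIST assessment during Cycles 1 to 5, and section 7.1.2 speaks of re-evaluation, not of scans. This helps less than it seems to. No imaging is scheduled in those cycles, section 7.1.2.1 accepts caliper measurement only for superficial lesions, and section 7.1.2.2 prefers imaging. The row cannot be relied on to give a response for a nasopharyngeal primary.

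Two points stand in full. First, that ORR uses the section 7.1.2 set is an inference, because section 8.4.3 names no denominator. It is the natural inference, since this is the only response-evaluable definition and the text goes on to say that these patients' responses are classified. If it is wrong, the denominator is undefined and the same edit is needed. Second, upward bias is not proven for every dropped patient. Someone who withdraws after completing definitive-intent chemoradiation may have responded. If unassessed patients responded at the same rate as the rest, the evaluable-set rate would not be biased.

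**Conclusion.** The point holds in a limited form. As written, the plan allows treated patients without a documented re-evaluation, and those with less than one cycle and no progression, to leave the ORR denominator, and no section counts them as non-responders. The direction is upward if those patients are mostly non-responders, which is plausible for early deaths and less certain for withdrawals. With 40 treated, 24 to 36 responders and every dropped patient a non-responder, the inflation runs from zero (all re-evaluated) through 3.2 to 4.7 points (two not) to 6.7 to 10.0 points (four not). These are assumed scenarios, not predictions.

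ORR is a secondary endpoint with no hypothesis, threshold or decision rule. The correction is worth making before analysis, but it does not affect the primary test.

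**What to change.** In section 8.4.3:
- Define the ORR denominator as all treated patients with measurable disease at baseline, and say what counts as treated.
- Add a not-evaluable category beside CR, PR, SD and PD, and count it as non-response.
- Report the rate in the section 7.1.2 re-evaluated set as a supportive analysis, with the number excluded and the reason for each.

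Reconcile section 7.1.2 with sections 8.2.5, 8.4.1 and 8.4.3, so that evaluable has one stated meaning for each endpoint.

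The cost is wording only. Measurable disease is already an entry criterion, so no new data are needed. The reported ORR may be slightly less favourable, and an unassessed patient who did respond is counted against the regimen; the supportive analysis shows how much that matters.
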